6.3 MEASURES TO MINIMIZE BIAS: RANDOMIZATION AND BLINDING

6.3.1 ALLOCATION TO STUDY INTERVENTION

After informed consent has been elicited from the subject or his/her legally authorized represented, and the subject is determined to fully meet the study eligibility criteria, he/she will be equally allocated (with a 1:1 ratio) to one of the following 2 treatment groups based on a permuted block randomization scheme with blocks stratified by site, age (22-69, 70-85) and mRS score at baseline (3 vs 4):

- BQ 2.0 active stimulation group
- BQ 2.0 sham stimulation group

Allocation (randomization) of participants to study groups will proceed through the use of the EDC system (Syncrony) for randomization and the BQ 2.0 Administrator Panel for treatment allocation. The site personnel (Study Coordinator or specified designee) will be required to enter or select information including but not limited to the user's ID and password, the protocol number, and the participant number. The site personnel will then be provided with a group assignment and randomization number. The Syncrony system will provide to the unblinded site personnel the study intervention allocation assigned. The randomization schedule and treatment arm assignments will be kept by Syntactx-NAMSA data manager with appropriate security measures and access control.

6.3.2 BLINDING OF SITE PERSONNEL AND SUBJECTS

	The efficacy of a frequency-tuned electromagnetic field treatment in facilitating the recovery of subacute ischemic stroke patients – a pivotal study		
	No. BQ5	Ver. 4	Page 55 of 150

This is a double-blind study, subjects and Investigators will be blinded to the device setting (Active/Sham). The study site team members receiving, storing, dispensing, preparing, and administering the study interventions will be blinded. Subjects' caregivers will also be blinded. There are no differences in the active and sham device appearance. Due to the non-invasive nature of the treatment, as well as the physical characteristic of the EMF, there is no noticeable difference between sessions conducted using an active or a sham device, facilitating full blinding of both subjects and Investigators.

BQ 2.0 does not produce any noticeable sound, light or sensation in connection with the stimulation which may disclose the arm assignment, making it ideal for testing in a sham-controlled setup. During sham treatment sessions, for purposes of maintaining the blind, the device will function as if it is delivering the therapy (i.e., the device will turn on and all indicators will function), but the frequency and intensity parameters that are not visible to the subject or site study members will be set to zero so that no stimulation is delivered. Furthermore, in the clinical trial setting, the data collected via the Qompass component of the device will not be accessible to blinded personnel or participants or used to actively monitor or optimize the dosage in order to maintain the blinding.

An authorized un-blinded individual at the site will be the only person to receive the group assignment of the randomized subject, and will enter the subject's group assignment to the study device, in accordance with the IFU and/or training received from the Sponsor. For more information, please refer to the Blinding Plan.

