2.2.2 SUMMARY OF CLINICAL RESEARCH OF THE BQ 2.0

Clinical investigations have been performed by BrainQ Technologies Ltd., in both stroke and spinal cord injury populations. In stroke patients, a pilot double-blind, parallel-group, randomized sham-controlled trial was performed (BQ3 trial) using the BQ 1.0 device, the direct predecessor of BQ 2.0.

This trial was performed at the BLK Super Specialty Hospital, a multi-specialty hospital located in Delhi, India. The study was supervised by an international contract research organization

(CRO) and conducted in conformance with GCP and in accordance with the principles of the Declaration of Helsinki. Ethics Committee (EC) approval was obtained before the study initiation. All subjects provided written informed consent to participate in the study.

The BQ3 trial enrolled patients diagnosed with a first ischemic stroke, with the diagnosis confirmed by imaging, and patients with a recurrent stroke in whom no previous neurological impairment in the same limb was reported before current stroke. Patients were recruited from 72 hours to 15 days from stroke onset or 21 days from stroke onset, in case the patient was still unstable at day 15. To be considered eligible, patient's FMA-UE had to be in the range of 10-45.

This trial was designed for a population of 50 but was terminated just short of the pre-specified interim analysis (planned at n=26; discontinued at n=25, with EC approval) due to the outbreak of COVID-19.

In total, 28 subjects were recruited to the study, of which 24 were randomized to receive either investigational (n=14) or sham therapy (n=10). Due to randomization error, which was revealed only post data lock and unblinding, two subjects received active treatment instead of sham treatment (n=16 and n=8, respectively). Of the 24 randomized subjects, 21 subjects completed all active (n=13) or sham (n=8) treatments (modified randomized as treated, mRT). To minimize bias, results of the mRT analysis are presented below (Figure 1).

[figure not shown]

Figure 1. Breakdown of BQ3 trial population, as stipulated and as implemented

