6.1.1.3 DESCRIPTION OF EACH COMPONENT

To achieve its purpose, BQ 2.0 ([Figure 6](#)) comprises the *DEVICE* and the *SOFTWARE APPLICATION* installed on *ANDROID* based *TABLET*:

1. *DEVICE* ([Figure 7](#)) – Wearable Device which includes: (1) embedded magnetic coils; (2) Waveform generator; (3) Rechargeable battery; and (4) the Qompass. The magnetic *COILS* are configured in three-dimensional shapes; with one *COIL* in the shape of a rectangle that goes along the spine, and two circle-shaped *COILS* that surround the brain. Custom plastic *COMBS* are used to ensure correct placement of the *COILS*. These are secured to a sheet of polypropylene. Also secured to the polypropylene are a custom box containing the printed circuit board which creates the wave function and a custom *BATTERY BOX* containing the battery to power the Device. The entire structure is covered in a layer of fabric which includes a *WAISTBAND* and *SHOULDER STRAPS* to secure the Device to the patient. *THE QOMPASS* ([Figure 8](#)) is a single-use sensor designed to be placed on the subject's forehead for the duration of each treatment session via an adhesive. It contains sensors that detect the electromagnetic field that the subject is exposed to, to ensure a subject receives the treatment as intended and allow for in depth monitoring and treatment optimization²⁶. Each unit is designed for one-time use to simplify the user experience.

Control of operation of the *DEVICE* is enabled through operation of the

2. *SOFTWARE APPLICATION* v. 5.0 and above ([Figure 9](#)) – (Android; Transmission Control Protocol/Internet Protocol (TCP/IP) communication), installed on an Android-based mobile device. The *SOFTWARE APPLICATION* controls the functionality of the *DEVICE*. Data collected is uploaded to a cloud compliant with the Health Insurance Portability and Accountability Act (HIPAA; implemented in 45 CFR Part 160 and Part 164, Subparts A and C) and the General Data Protection Regulation (GDPR; Regulation (EU) 2016/679). Data upload is performed strictly for backup purposes. No data interpretation is conducted on the cloud.

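### No unblinded role is asked to compare the recorded field with the assigned arm, so a wrongly set device might not be found until after unblinding

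*Protocol*

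**What the plan says.** **Pilot (Protocol 2.2.2).** Of 24 randomized subjects, 14 were assigned to active and 10 to sham. The protocol then reports: "Due to randomization error, which was revealed only post data lock and unblinding, two subjects received active treatment instead of sham treatment". As treated, the split became 16 and 8. The pilot used the predecessor device, BQ 1.0.

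**Setting the arm (6.3.1, 6.3.2, 6.2.4).** The EDC system randomizes and the BQ 2.0 Administrator Panel is used for treatment allocation. One unblinded individual at the site "will be the only person to receive the group assignment of the randomized subject" and enters it into the device. Each device is tested before it is allocated to a participant. Active and sham devices look alike, all indicators work in both arms, and the field parameters are hidden from subjects and site study members.

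**The sensor (6.1.1.3).** The Qompass is placed on the "forehead for the duration of each treatment session via an adhesive". "It contains sensors that detect the electromagnetic field that the subject is exposed to", and the stated purpose includes "to ensure a subject receives the treatment as intended".

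**The restriction (6.3.2 and footnote 26).** Section 6.3.2 says that the data "will not be accessible to blinded personnel or participants or used to actively monitor or optimize the dosage in order to maintain the blinding". Footnote 26 says that in the trial they are collected and nothing more. The only planned analysis of them is exploratory: adherence against outcome (9.4.9).

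**Analysis sets (9.3, 9.4.6).** The principal efficacy set and the interim analysis use the mITT set, as randomized. The PP and safety sets are as treated; no source for the treatment actually received is named.

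**The concern.** The sponsor has already had subjects receive the wrong arm without anyone noticing until the blind was broken. The present set-up again depends on a manual entry by one person. The device test cannot confirm that entry because it comes first, and nobody present at a session can see a mistake. The one instrument that could show it runs in every session, but its output is set aside for the duration of the trial.

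The reason given is to protect the blind. That justifies closing the data to blinded staff and participants. It is not a reason to leave them unused by people who already know the allocation.

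At stake is the principal comparison. A sham subject who receives the field still counts as sham in the mITT set, so the observed difference shrinks. The same data feed the interim decision, which can stop the trial for futility. An error found at the start of treatment costs little; one found after lock may have affected all 45 sessions.

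**Working it through.** **Inputs.** Section 9.2: difference 0.5, SD 1, 1:1 allocation, two-sided 5%, two-sample t-test, 64 per arm. Section 9.4.6: interim at 78 of 128 evaluable, futility stop if conditional power is below 32.7375%. Section 2.2.2: 2 of 10 sham subjects crossed (20%; 2/24 = 8.3% of all randomized). The crossover share f in this trial is assumed.

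**1. The plan's own figure.** Noncentrality = 0.5 / √(2/64) = 2.828, with 126 degrees of freedom and critical t 1.979. Power is 80.1%, so 64 per arm (128 in total) is reproduced.

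**2. Effect of crossover at a fixed 64 per arm.** If a share f of the sham arm receives active treatment and is analyzed as sham:

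- expected difference = 0.5 × (1 − f)
- sham variance = 1 + f(1 − f) × 0.5², because that arm is now a mixture
- pooled SD = √[(1 + sham variance)/2]

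| Sham subjects crossed | f | Difference | Pooled SD | Power |
|---|---|---|---|---|
| none | 0 | 0.500 | 1.000 | 80.1% |
| 2 of 64 | 0.031 | 0.484 | 1.002 | 77.5% |
| 10% | 0.10 | 0.450 | 1.006 | 71.0% |
| 20% (pilot share) | 0.20 | 0.400 | 1.010 | 60.4% |

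Holding the SD at 1 changes little: 71.4% at f = 0.10 and 61.2% at f = 0.20. To keep 80% power, the evaluable total would have to be 160 at f = 0.10 and 204 at f = 0.20.

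**3. Effect on the futility stop.** This uses conditional power at the observed trend and a normal approximation. With information fraction t = 78/128 = 0.609, conditional power = Φ[(z₁/√t − 1.96)/√(1 − t)]. Setting it to 0.327375, whose normal quantile is −0.447, gives z₁ = 0.781 × (1.96 − 0.447 × 0.625) = 1.31. The trial stops if z₁ is below that. With 39 per arm, the mean of z₁ is difference / (SD × √(2/39)):

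| f | Mean of z₁ | Chance of futility stop |
|---|---|---|
| 0 | 2.21 | 19% |
| 0.10 | 1.98 | 25% |
| 0.20 | 1.75 | 33% |

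**4. Is any check described?** The protocol names several unblinded parties: the data manager who keeps the schedule (6.3.1, 6.3.4), the site individual (6.3.2), the independent statistician (6.3.3, 9.4.6), the DSMB (9.4.6) and a possible sponsor representative (6.3.3). None is given the task of comparing delivered field with assigned arm.

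**The case against.** A reader might infer that the protocol forbids any use of the sensor data to verify the arm. The text does not go that far. Section 6.3.2 limits access by blinded people and use for monitoring or optimizing the dosage. It does not expressly prohibit an arm check by someone unblinded. Footnote 26, by confining the data to collection, points against such a check, but the accurate statement is that nobody is assigned one.

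A reader might also infer that a repeat would go undetected altogether. That is not supported either: the data are kept for the exploratory adherence analysis, where a sham subject with a recorded field could be seen. The risk is late detection.

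Nor is it shown that the pilot's mechanism would recur. The pilot was a single-site study on an earlier device, its mechanism is not stated, and allocation here runs through a different system. An error in the allocation list itself would pass the proposed check, because list and field would agree.

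The Blinding Plan, to which 6.3.2 refers, is not at hand and may contain a set-up check. The 20% rests on two events in ten (exact 95% interval about 3% to 56%), and the sample size can rise to 292 evaluable, so the fixed-sample powers are not the power of this adaptive design. Finally, 10.1.10 treats deviations in Qompass use as non-significant, so some readings may be missing, and the protocol gives no detection accuracy for the sensor.

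All of these points limit the claim. None supplies the missing task in the protocol.

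**Conclusion.** The point holds as a gap in safeguards, not as a contradiction. The protocol records an earlier unnoticed arm error, relies on one manual entry that the described device test cannot verify, and assigns no unblinded role to compare the field recorded in each session with the randomized arm. A wrongly set device might therefore not be found until after unblinding.

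The size depends on an unknown rate. At a fixed 64 per arm, two crossed subjects cost under three points of power (80.1% to 77.5%), while the pilot's share of 20% would bring power to about 60%. At that share the chance of a futility stop under a true 0.5-point effect would rise from about 19% to about 33%. These figures assume that crossed sham subjects gain the full active effect, that errors go only from sham to active, and, for the interim, that conditional power is taken at the observed trend. The change is worth making because the sensor and the unblinded roles already exist.

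**What to change.** Amend 6.3.2 and footnote 26, and align the Blinding Plan. If that plan already holds such a check, reconcile the footnote with it.

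- Keep Qompass data closed to blinded staff, participants and the sponsor's study team, and do not use them to adjust dosage.
- Have a role that is already unblinded (the data manager holding the schedule, or the independent unblinded statistician) compare field present or absent with the randomized arm. Do this after each subject's first session with a usable reading and after any device replacement.
- Send a mismatch only to the site's unblinded individual, to restore the randomized setting, and log it under restricted access.
- In 9.3, name this record as the source for treatment actually received in the PP and safety sets.

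**Cost.** One more firewalled data flow. It is a new function, since 6.1.1.3 describes the cloud upload as backup with no interpretation of data there. There is a small risk that a correction hints at allocation to people around the subject. The check gives no protection against an error in the allocation list.

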6.3.3 BLINDING OF THE SPONSOR

The Sponsor, the sites and the study statistician will remain blinded throughout the study. This blinding will include the interim analysis results as well; only the decision made will be shared. An independent unblinded statistician (not the study statistician) will perform the assessments for the interim analysis. An unblinded representative of the Sponsor may be designated as well.

For unblinding procedures in place for the planned interim data analysis, please refer to § 9.4.6. as well as to the Unblinding Plan.

6.3.4 BREAKING THE BLIND

The randomization schedule and treatment arm assignments will be kept by Syntactx-NAMSA data manager with appropriate security measures and access control. In case of an emergency, the Investigator has the sole responsibility for determining if unblinding of a subject's study intervention assignment is warranted. Subject safety must always be the first consideration in making such a determination. If the Investigator decides that unblinding is warranted, the

	The efficacy of a frequency-tuned electromagnetic field treatment in facilitating the recovery of subacute ischemic stroke patients – a pivotal study		
	No. BQ5	Ver. 4	Page 56 of 150

Investigator should make every effort to contact the Sponsor prior to unblinding a subject's group assignment, unless this could delay further management of the subject. If a subject's group assignment is unblinded, the Sponsor must be notified within 24 hours after breaking the blind. The date and reason that the blind was broken must be recorded in the source documentation and communicated to the sponsor in a formal communication medium.

6.4 STUDY INTERVENTION COMPLIANCE

Following intervention, appropriate CRF must be filled in, within the time frame for completion as specified in [Table 5](#). The date and time of each treatment administered will be recorded in the source documents and recorded in the CRF. The study Monitor will check the CRF against the accountability log and related treatment session worksheets used by the site to verify the number of devices dispensed on a per-subject basis.

6.5 CONCOMITANT THERAPY

All sites will provide concomitant medical therapies to prevent recurrent stroke and conventional rehabilitation therapy to maximize recovery from the index stroke according to United States national guidelines ([43](#), [74](#), [75](#)).

All concomitant prescription medications, over-the-counter medications, and supplement medications taken during study participation will be recorded on the appropriate CRFs. For this protocol, a prescription medication is defined as a medication that can be prescribed only by a properly authorized/licensed clinician.

6.5.1 RESCUE MEDICINE

Not applicable.

7 STUDY INTERVENTION DISCONTINUATION AND PARTICIPANT DISCONTINUATION/WITHDRAWAL

7.1 DISCONTINUATION OF STUDY INTERVENTION

Any symptoms of treatment-emergent clinical deterioration in subject's condition requiring intervention of the medical team to alleviate these symptoms and qualifying for toxicity Grade 3 (or higher) on the CTCAE v.5.0 scale will result in a halt of administration of the study intervention for that treatment session; halting for a longer period of time will occur only if deemed necessary by the Investigator.

In general, discontinuation of administration of the study intervention, for any reason, does not mean discontinuation from the study, and the remaining study procedures should be completed as indicated by the study protocol, unless informed consent is withdrawn. If a clinically significant finding is identified (including, but not limited to changes from baseline) after enrollment, the Investigator or qualified designee will determine if any change in subject management is needed. Any new clinically relevant finding will be reported as an AE. For requirements on reporting of adverse events, serious adverse events and unanticipated problems please refer to §§ 8.3.5, 8.3.6, and 8.4.2, respectively.

The data to be collected at the time of discontinuation of administration of the study intervention will include the date and reason for discontinuation and any data on the adverse event(s), if applicable.

Women who become pregnant during the trial will continue to be assessed, including assessment of pregnancy outcomes, and investigational device administration will be discontinued. Further provisions on reporting of pregnancy, including period of reporting are in § 8.3.9.

7.2 PARTICIPANT DISCONTINUATION/WITHDRAWAL FROM THE STUDY

Participants are free to withdraw from participation in the study or discontinue the study intervention at any time upon request. Those wishing to discontinue participation do not have to provide a reason; however, when appropriate, the site investigator should discuss the study, informed consent, and any on-going risks and benefits to continued participation with the participant.

In addition to discontinuation of administration of the study intervention (section 7.1), subject participation in the study may be terminated by the Investigator or the Sponsor if any one or more of the following conditions are met:

- occurrence of an unexpected serious adverse event;

	The efficacy of a frequency-tuned electromagnetic field treatment in facilitating the recovery of subacute ischemic stroke patients – a pivotal study		
	No. BQ5	Ver. 4	Page 58 of 150

- pregnancy;
- loss to follow-up (refer to § 7.3 for accompanying instructions); health conditions that require treatment that might affect the procedure and/or its outcome;
- significant protocol deviation (please refer to § 10.1.10) or noncompliance, either on the part of the subject or Investigator. These will include (but not limited to):
 - o enrollment in violation of the study eligibility criteria;
 - o performing the trial procedure not as prescribed in the BQ 2.0 IFU;
 - o other ethical or clinical considerations at the discretion of Investigator.
 - o enrollment in another interventional study overlapping with the period of participation in this study.

Data collected prior to withdrawal of consent will remain in the study database, but no further data will be collected on those who withdraw. Follow up on serious adverse events that are not resolved by the time that the subject leaves the study will be handled as defined in § 8.3.4. Follow up on pregnancy outcome will be handled as defined in § 8.3.9.

Withdrawn/discontinued randomized subjects will not be replaced.

If a subject withdraws from the clinical investigation, the reason(s) shall be recorded. Withdrawals will be recorded, analyzed, and reported to local IRBs/ECs as required.

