9.2 SAMPLE SIZE DETERMINATION

A sample size is calculated to test the null hypothesis with 80% power at a 5% two-sided level of significance using a two sample-t-test for simplicity, even though the main statistical analysis may employ a statistically more powerful model-based approach. The estimates used for the mean and standard deviation of the changes from baseline to day 90 are taken from the literature as well as company pilot study data. In the pilot study, the mean change in mRS score from baseline to week 9 in the treatment group was -2.5 (SD=0.66) versus -1.3 (SD=0.46) in the sham group. In the literature a difference of 0.06 points on the mRS between treatment groups is considered clinically meaningful (114). As powering the trial to detect this difference would yield infeasibly large sample sizes, sample size projections were based on detecting a difference as low as 40% of the difference seen in the pilot trial = 0.5-point. To detect a 0.5-point difference between the groups with 80% power at a 5% level of significance using a standard deviation of 1 point and 1:1 allocation ratio, the calculated sample size (PROC POWER in SAS V9.4) is 128 participants in total, 64 participants in each arm. Allowing for a 15% dropout, 150 participants should be randomized.

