9.4.2 ANALYSIS OF THE PRIMARY ENDPOINT

The primary endpoint, mRS change from baseline (day 4-21 post-stroke) to 90 days post-stroke, will be compared between the treatment groups using repeated measures analysis of covariance (ANCOVA, SAS® MIXED procedure).

The model will include the following fixed effects: treatment group, visit [categorical – midterm follow-up visit (± 4 days from 20th treatment) and Day 90 follow-up visit (day 90 ± 15 days post-stroke)], treatment group by visit interaction with baseline mRS and age entered as covariates. Age will be entered as a continuous variable so that the potential for co-linearity problems will be minimized. Center will be entered as a random effect. The treatment group by site interaction will be evaluated as well, but not as part of the principal statistical evaluation.

The compound symmetry covariance structure will be used. If the model does not converge, then either the unstructured or autoregressive (AR1) (whichever model has the lower Akaike information criterion statistic) covariance matrix structure will be used instead. At this time point (up to 3 months post stroke), we do not expect a high proportion of dropouts, as a placebo effect of the sham treatment is expected and was taken into consideration in the design of the study. Thus, any missing data at this time point can be considered missing at random. Therefore, since likelihood based repeated measures is also an imputation method, for this evaluation no other method of imputation of missing data is considered beyond the model estimates. Nevertheless, should the missing at random assumption prove to be incorrect, a sensitivity analysis using methods for data imputation may be performed, such as last observed value (LOV) of that endpoint (115). The LOV is defined as the last available post baseline visit data up to and including the last treatment visit or termination visit. Additionally, we may consider multiple

	The efficacy of a frequency-tuned electromagnetic field treatment in facilitating the recovery of subacute ischemic stroke patients – a pivotal study		
	No. BQ5	Ver. 4	Page 81 of 150

imputation using a model incorporating key baseline prognostic features as well as the last post-randomization if deemed necessary.

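### Section 7.2 permits ending a randomized subject's participation on grounds that can be outcome-related, and the protocol asks for no day-90 mRS afterwards although the primary analysis assumes missing at random

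*Protocol*

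**What the plan says.** Section 7.1 deals with stopping the device. As a general rule, "discontinuation of administration of the study intervention, for any reason, does not mean discontinuation from the study", and the remaining procedures are to be completed; withdrawal of consent is the only exception named. On pregnancy it is specific: "Women who become pregnant during the trial will continue to be assessed", with the device stopped.

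Section 7.2 adds a separate power, under which "subject participation in the study may be terminated by the Investigator or the Sponsor if any one or more of the following conditions" are met. The list contains an unexpected SAE, pregnancy, loss to follow-up, health conditions whose treatment might affect the procedure or its outcome, and significant deviation or noncompliance by subject or Investigator. The last group includes eligibility violations, use outside the instructions for use, Investigator discretion on ethical or clinical grounds, and enrolment in another interventional study. Subjects who leave are not replaced. Section 6.1.2 refers to 7.2 for treatment-schedule disruptions that lead to withdrawal, but 7.2 names none.

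Section 10.1.9.1, on data to be collected after termination or withdrawal, requires case report forms, follow-up included, only up to that point.

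Section 9.3 makes mITT, analyzed as randomized, the principal efficacy set. Section 9.4.2 uses a likelihood-based repeated-measures model and states that "any missing data at this time point can be considered missing at random". The reasons given are few expected dropouts and a placebo effect of sham. It adds multiple imputation from baseline features and the last observed value, and LOCF as a sensitivity analysis.

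**The concern.** An as-randomized analysis needs the day-90 mRS of every randomized subject who has started treatment, whatever happened to the treatment. Section 7.2 lets someone other than the subject end follow-up, and two of its grounds, an unexpected SAE and a health condition needing treatment, plausibly mark subjects who will do worse than their earlier scores suggest. If their day-90 outcome is not collected, the missing-at-random assumption is weakest for exactly these subjects. The reasons that section 9.4.2 gives for the assumption do not consider these terminations.

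At stake is a shift in the treatment difference if such terminations, or the prognosis of those terminated, differ between arms. The loss is also avoidable: these subjects have not withdrawn consent, and the day-90 visit is already scheduled.

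**Working it through.** **The passages side by side**

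- *Pregnancy.* Section 7.1 says that assessment continues; section 7.2 lists pregnancy as a ground for ending participation. Both cannot be followed if the power in 7.2 is used. The cross-reference in 7.2 to section 8.3.9 preserves follow-up of the pregnancy outcome, not of the mRS.
- *Other grounds.* Section 7.1 is qualified as a general rule, and 7.2 is framed as additional to it and as permissive. This is tension with a principle, not a flat contradiction.
- *Is the outcome lost?* The sentence in 7.2 that ends data collection refers to subjects who withdraw. Section 10.1.9.1 treats termination in the same way as withdrawal and asks for nothing after it. A subject terminated before day 90 therefore has no required day-90 mRS. One terminated before the midterm visit has no scheduled post-baseline mRS at all.
- *Does the analysis repair it?* The repeated-measures model uses baseline and midterm mRS and is valid under missing at random. The multiple imputation, as described, rests on the same assumption. LOCF freezes the last score of a patient who may still be changing. None of these is an explicit not-at-random analysis.

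**The plan's own figure**

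Inputs from section 9.2: difference 0.5 mRS points, SD 1, equal allocation, two-sided alpha 5%, target power 80%. The stated result is "128 participants in total, 64 participants in each arm". A two-sample t-test (noncentral t) gives 79.5% power at 63 per arm and 80.1% at 64, so the figure reproduces. For dropout, 128/0.85 = 150.6 (stated 150, a rounding matter) and 292/0.85 = 343.5 (stated 344). The sample size is not in dispute.

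**Illustration of the possible shift**

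Let p be the share terminated without a day-90 mRS and D the number of points by which their unobserved day-90 mRS is worse than its missing-at-random prediction. Each arm's mean improvement is then overstated by p × D, so

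shift = p(active) × D(active) − p(sham) × D(sham).

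The protocol gives neither p nor D; the values below are **assumed**. With equal D in both arms, p = 10% active and 5% sham, SD 1, SE = √(2/n per arm), and no true effect:

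| D (assumed) | Shift = 0.05 × D | Share of the 0.5-point design effect | Two-sided rejection, 64 per arm | Two-sided rejection, 146 per arm |
|---|---|---|---|---|
| 0.5 | 0.025 | 5% | 5.2% | 5.5% |
| 1 | 0.05 | 10% | 5.9% | 7.1% |
| 2 | 0.10 | 20% | 8.7% | 13.7% |

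Rejection rate = 1 − Φ(1.96 − shift/SE) + Φ(−1.96 − shift/SE), with SE = 0.177 at 64 per arm and 0.117 at 146 per arm (the maximum of 292). As an anchor for D, section 2.2 cites an average improvement of about 1.1 points; a subject predicted to improve by that much who does not improve has D = 1.1, giving 0.05 × 1.1 = 0.055.

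If p and D are equal in both arms, the shift is 0. If more subjects are terminated on sham, the shift favors sham.

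**The case against.** There is a good deal on the other side.

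- Section 7.2 permits termination; it does not require it. A reader might infer that 7.2 as a whole contradicts 7.1, or that any SAE ends participation. The text does not support either: only pregnancy clashes directly, and the SAE must be unexpected. This stands. Pregnancies should also be few, given ages 22 to 85 and the contraception criterion.
- A reader might take every listed ground as outcome-related. Eligibility violations, use outside the instructions, Investigator noncompliance and enrolment in another study have no stated link to day-90 mRS. This stands; the argument rests on the unexpected SAE and the health-condition ground.
- The model draws on each subject's own midterm mRS where there is one, so some of this missingness may be at random given the observed data. This stands, and it is why D is defined as departure from that prediction.
- Nothing in the protocol predicts more terminations on active. Investigators and subjects are blinded, and the pilot reported no device- or procedure-related adverse events. This stands against any claim that the trial is biased towards the device. It does not exclude differences driven by events.
- A reader might infer a power loss, for example from 80% to about 75% at 112 evaluable, by adding a further 10% loss to the 15% allowance. Section 9.2 does not restrict that allowance by cause, so terminations under 7.2 fall within it. No further loss is shown.
- A statistical analysis plan may add not-at-random analyses. It may, but it cannot supply outcomes that were not collected.

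**Conclusion.** The point holds as a defect of wording with a statistical consequence. Section 7.2, read with 10.1.9.1, permits follow-up of a consenting randomized subject to end before day 90 on grounds that can be tied to outcome, while section 9.4.2 assumes missing at random without considering these cases. The contradiction is direct for pregnancy and one of principle for the rest.

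The size is unknown. Under the assumed 10% versus 5% and departures of 0.5 to 2 points, the difference shifts by 0.025 to 0.10 mRS points, which is 5% to 20% of the design effect; under equal rates and equal departures it does not shift. A reader might set such figures against the 0.06 points that section 9.2 cites as clinically meaningful and conclude that the trial will mislead. The documents do not support that: the rates are invented for illustration, and 9.2 sets 0.06 aside as a design target in favor of 0.5. The change is worth making because it removes an avoidable dependence on an untestable assumption at very little cost.

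**What to change.** Reconcile sections 6.1.2, 7.1, 7.2 and 10.1.9.1, including the two statements on pregnancy and the reference in 6.1.2 to schedule disruptions that 7.2 does not list. State that, after termination by the Investigator or Sponsor without withdrawal of consent, the day-90 mRS is still sought and is used in the ITT and mITT analyses. Section 8.1.1.6 already allows that visit to be held remotely, by audio alone if necessary, in special circumstances with the Principal Investigator's approval. Keep this subject to the rule in section 5.5 that ends participation for a subject who becomes a prisoner. Deviations continue to be handled through the per-protocol set in section 9.3.

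No closed list of exit reasons is needed, and no position is taken on when the intervention or participation should stop; that discretion is left as it is. The cost is protocol wording and a few additional day-90 contacts.
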